APPENDIX 6. SCHEDULE OF ASSESSMENTS

Study procedures	Screening (within 28 days prior to first dose)	Periods 1 and 2			Follow-up telephone call (Period 2, Days 13 to 15)
		Day -1	Days 1 to 4	Day 8 (168 hours postdose)/ Early termination	
Assessment/Administrative procedures:					
Informed consent	X				
Inclusion/exclusion criteria	X				
Medical history, demographic data	X				
Urinary drug screen (including cotinine)	X	X			
Alcohol test		X			
Serology	X				
TSH testing	X				
Height and body weight	X ^a	X			
COVID-19 swab collection & analysis	X				
Study residency:					
Check-in		X			
Check-out			Day 4 (72 hours postdose)		
Nonresidential visit	X			X	
Study drug administration:			Day 1 (0 hour)		
Pharmacokinetics:					

Study procedures	Screening (within 28 days prior to first dose)	Periods 1 and 2			Follow-up telephone call (Period 2, Days 13 to 15)
		Day -1	Days 1 to 4	Day 8 (168 hours postdose)/ Early termination	
Blood sampling ^b			Predose (-0.5), 0.5, 1, 2, 4, 6, 8, 12, 24, 48, and 72 hours postdose	X	
Safety and tolerability:					
Adverse event recording	X	X	Ongoing	X	X
Prior/concomitant medication monitoring	X	X	Ongoing	X	X
Clinical laboratory evaluations ^c	X	X	Day 4	X (Period 2 only or early termination, if applicable)	
Vital signs (supine) ^d	X	X	Predose, 4, 24, 48, and 72 hours postdose	X	
Single 12-lead ECG ^e	X	X	Predose, 4, and 72 hours postdose	X	
Physical examination	X	X ^f	Day 4 ^g	X ^g	

Abbreviations: ECG = electrocardiogram; PK = pharmacokinetic; QTcF = QT interval corrected for heart rate using Fridericia's method; TSH = thyroid-stimulating hormone.

Note: The minimum washout period between dose administrations will be 14 days.

a. Height measured at Screening only.

b. PK blood sampling: predose (within 30 minutes prior to dosing) and 0.5, 1, 2, 4, 6, 8, 12, 24, 48, 72, and 168 hours post-dose, a total of 12 samples in each study period. The allowed time window will be ± 2 minutes for the post-dose timepoints ≤ 12 hr, ± 10 minutes for 24 to 72 hr post-dose, and ± 2 hr for 168 hr post-dose.

c. Blood and urine samples will be collected (hematology, chemistry, and urinalysis) for clinical laboratory evaluations. Samples for serum chemistry will be obtained following a fast of at least 8 hours; however, in the case of dropouts or rechecks, subjects may be permitted not to have fasted for 8 hours before the serum chemistry sample is taken.

d. Blood pressure and pulse rate, respirations, and oral body temperature. Subjects must be supine for at least 5 minutes before blood pressure and pulse rate measurements. The assessment will be performed after ECG, with the allowed time window of within 3 hr before dose administration for predose time point, ± 20 minutes for the 4 hr post-dose, and ± 30 minutes for 24 hr, 48 hr and 72 hr post-dose.

e. Electrocardiograms are to be performed as close to PK sampling time as possible and followed by vital assessment. The allowed time window will be within 3 hr before dose administration for Predose, and ± 20 minutes for the 4 hr postdose, and ± 30 minutes for the 72 hr postdose. Assessments will include an evaluation of heart rate, QT, and QTc intervals. RR interval should be recorded during each ECG assessment in order to calculate QTcF. ECGs are to be

- performed prior to collection of vital signs and PK sample collection blood draws. Single 12-lead ECGs will be repeated twice, and an average taken of the 3 readings, if either of the following criteria apply: QTcF >500 msec OR QTcF change from the baseline (predose) is >60 msec.
- f. Full physical examination at Check-in for Period 1; symptom-directed physical examination at Check-in for Period 2.
 - g. Symptom-directed physical examination.

1.1 Rationale

Sitravatinib (MGCD516) is an orally available, potent small-molecule inhibitor of a closely related spectrum of tyrosine kinases. This subset of tyrosine kinases is involved in several processes implicated in human cancer, including regulation of tumor growth and cell survival pathways, tumor invasion and metastatic progression, as well as tumor angiogenesis. Antitumor activity of sitravatinib has been observed in several human tumor xenograft models exhibiting genetic alterations in receptor tyrosine kinase targets, providing the rationale for evaluating sitravatinib monotherapy in tumors driven by these pathways in the clinical setting. Additionally, based on its tyrosine kinase target profile, sitravatinib may modulate effects on the tumor microenvironment to overcome resistance to checkpoint inhibitors by effects on relevant immune cell populations. These effects are predicted to complement and augment the activity observed with checkpoint inhibitor therapy (CIT).

In clinical studies, sitravatinib has been administered as a single agent in the ongoing first-in-human Study 516-001 and in Study 516-006 (Mirati Therapeutics, Inc.).

Study 516-001 is an ongoing multicenter, Phase 1/1b clinical study characterizing the safety, pharmacokinetics (PK), metabolism, the pharmacodynamic, and clinical activity of sitravatinib in patients with advanced solid tumors. The primary objective of the Phase 1 study was the determination of the maximum tolerated dose (MTD), while Phase 1b objectives included assessment of safety and clinical activity in patients with certain tumor types (e.g., renal cell carcinoma) or with tumors characterized by certain genetic alterations. The MTD was identified as 150 mg once daily (QD), and based on long-term tolerability observed in patients enrolled into Study 516-001 treated with 120 or 150 mg QD, the Sponsor selected 120 mg QD as the current recommended Phase 2 dose, using the sitravatinib free base capsule formulation.

Study 516-006 is an open-label, two part, phase 1 study assessing relative bioavailability and pharmacokinetics (PK) of a single oral dose of sitravatinib administered as free base capsules (reference formulation) and malate salt capsules (test formulation, developed by Mirati) in healthy male subjects. The primary objective is to investigate the relative bioavailability and PK of sitravatinib free base and malate salt capsule formulations following oral administration in healthy subjects. The results showed that PK exposure of 100 mg sitravatinib malate salt capsule (roller compaction) was comparable with 120mg free base capsule.

In order to introduce BeiGene malate salt capsule formulation (roller compaction) into the development of sitravatinib in China, this study will be conducted to compare the systemic exposure of sitravatinib between the malate salt capsule (roller compaction, manufactured by BeiGene) and the free base formulation. The primary objective of the study is to evaluate the relative bioavailability and PK of the different formulations.

The sitravatinib doses in this study are based on the results from study 516-006. To ensure comparable exposures, the free base reference dose will be 120 mg and the malate salt capsule dose will be 100 mg. The exposure ratio information will be used to guide the dose for the selected malate salt capsule formulation needed to achieve exposure comparable to the recommended Phase 2 dose (RP2D) of the free base product.

Doses of 100 or 120 mg sitravatinib proposed in this study are considered safe and appropriate for the evaluation of sitravatinib PK profiles in healthy subjects.

2. Summary of the Protocol

2.1 Study Objectives

2.1.1 Primary Objective

The primary objective of the study is to investigate the relative bioavailability and PK of sitratvatiniib free base and malate salt capsule formulations following oral administration in healthy subjects.

2.1.2 Secondary Objectives

The secondary objective of the study is to assess the safety and tolerability of single-dose free base and malate salt capsule formulations of sitratvatiniib in healthy subjects.

2.2 Study Endpoints

2.2.1 Primary Endpoints

The following PK endpoints will be evaluated during this study:

- AUC from time zero to infinity (AUC_{0-inf})
- AUC from time zero to the last quantifiable concentration (AUC_{0-t})
- Maximum observed concentration (C_{max})
- Time of the maximum observed concentration (T_{max})
- Half-life ($t_{1/2}$)
- Apparent total plasma clearance (CL/F)
- Apparent volume of distribution (V_z/F)
- Dose-normalized AUC_{0-inf} , AUC_{0-t} and C_{max} .

Other PK parameters may also be reported as appropriate.

2.2.2 Secondary Endpoints

The safety outcome measures for this study are as follows:

- Incidence and severity of AEs
- Incidence of laboratory abnormalities, based on hematology, clinical chemistry, and urinalysis test results
- 12-lead electrocardiogram parameters
- Vital sign measurements
- Physical examinations.

2.3 Study Design

This will be a phase 1, open-label study using a two-period crossover design to compare the bioavailability and PK of the free base formulation at 120 mg and the malate salt capsule formulation (roller compaction, manufactured by BeiGene) at 100 mg after a single oral administration to healthy male subjects.

Subjects will be randomized into one of two sequences and will participate in two dosing periods (Table 1). The minimum washout period between dose administrations will be 14 days. Up to 26 subjects (include ≥ 16 Asian subjects) will be enrolled to guarantee that at least 24 subjects complete the study.

Table 1 Dosing Sequences

Dosing sequence	Period 1	Washout (minimum)	Period 2
1 N=13	120 mg sitravatinib free base capsule	14 days	100 mg sitravatinib malate salt capsule
2 N=13	100 mg sitravatinib malate salt capsule	14 days	120 mg sitravatinib free base capsule

N: number of subjects

Potential subjects will be screened to assess their eligibility to enter the study within 28 days prior to the first dose administration. In Periods 1 and 2, subjects will be admitted into the Clinical Research Unit (CRU) on Day -1 and will stay in the CRU until discharge on Day 4. In each period, subjects will attend a nonresidential visit on Day 8 for PK (168 hours post-dose) sampling. Subjects will receive a Follow-up phone call on Days 13 to 15 of Period 2. A Schedule of Assessments is presented in Table 2.

The total duration of study participation for each subject (from Screening through Follow-up phone call) is anticipated to be up to approximately 8 weeks.

The start of the study is defined as the date the first enrolled subject signs an Informed Consent Form (ICF). The point of enrollment occurs at the time of randomization number allocation. The end of the study is defined as the date of the last subject's last assessment (scheduled or unscheduled).

2.4 Sample Size Determination

Up to 26 subjects (13 per dosing sequence) will be enrolled to guarantee that at least 24 subjects complete the study. The number of subjects is justified in powering the study to delineate comparability of the sitravatinib mean exposure between the two dose formulations. Assuming an intrasubject coefficient of variation (CV%) of 40% (which was the maximum CV% observed on C_{max} in previous study), and a malate salt capsule to free base ratio of $100 \pm 5\%$, 24 subjects in a two-way crossover design will provide a probability of 92% for the ratio of geometric means (malate salt to free base) to be within the 80% to 125% limits if the true ratio is between 95% and 105%. The conclusions in the clinical study report will be drawn based on the estimated ratios of geometric means only and the 90% confidence intervals (CIs) will be presented for informational purposes.

2.5 Schedule of Assessments

Table 2 presents the schedule of study events for Treatment Periods 1 and 2.

Statistical Analysis Plan

Sponsor: BeiGene, Ltd.
Protocol Number: BGB-Sitravatin b-101

Table 2 Schedule of Assessments

Study procedures	Screening (within 28 days prior to first dose)	Periods 1 and 2			Follow-up telephone call (Period 2, Days 13 to 15)
		Day -1	Days 1 to 4	Day 8 (168 hours postdose)/ Early termination	
Assessment/Administrative procedures:					
Informed consent	X				
Inclusion/exclusion criteria	X				
Medical history, demographic data	X				
Urinary drug screen (including cotinine)	X	X			
Alcohol test		X			
Serology	X				
TSH testing	X				
Height and body weight	X ^a	X			
COVID-19 swab collection & analysis	X				
Study residency:					
Check-in		X			
Check-out			Day 4 (72 hours postdose)		
Nonresidential visit	X			X	
Study drug administration:			Day 1 (0 hour)		
Pharmacokinetics:					

Statistical Analysis Plan

Sponsor: BeiGene, Ltd.
Protocol Number: BGB-Sitravatin b-101

Study procedures	Screening (within 28 days prior to first dose)	Periods 1 and 2			Follow-up telephone call (Period 2, Days 13 to 15)
		Day -1	Days 1 to 4	Day 8 (168 hours postdose)/ Early termination	
Blood sampling ^b			Predose (-0.5), 0.5, 1, 2, 4, 6, 8, 12, 24, 48, and 72 hours postdose	X	
Safety and tolerability:					
Adverse event recording	X	X	Ongoing	X	X
Prior/concomitant medication monitoring	X	X	Ongoing	X	X
Clinical laboratory evaluations ^c	X	X	Day 4	X (Period 2 only or early termination, if applicable)	
Vital signs (supine) ^d	X	X	Predose, 4, 24, 48, and 72 hours postdose	X	
Single 12-lead ECG ^e	X	X	Predose, 4, and 72 hours postdose	X	
Physical examination	X	X ^f	Day 4 ^g	X ^g	

Abbreviations: ECG = electrocardiogram; PK = pharmacokinetic; QTcF = QT interval corrected for heart rate using Fridericia's method; TSH = thyroid-stimulating hormone.

Note: The minimum washout period between dose administrations will be 14 days.

a. Height measured at Screening only.

b. PK blood sampling: predose (within 30 minutes prior to dosing) and 0.5, 1, 2, 4, 6, 8, 12, 24, 48, 72, and 168 hours post-dose, a total of 12 samples in each study period. The allowed time window will be ±2 minutes for the post-dose timepoints ≤ 12 hr, ±10 minutes for 24 to 72 hr post-dose, and ±2 hr for 168 hr post-dose.

c. Blood and urine samples will be collected (hematology, chemistry, and urinalysis) for clinical laboratory evaluations. Samples for serum chemistry will be obtained following a fast of at least 8 hours; however, in the case of dropouts or rechecks, subjects may be permitted not to have fasted for 8 hours before the serum chemistry sample is taken.

d. Blood pressure and pulse rate, respirations, and oral body temperature. Subjects must be supine for at least 5 minutes before blood pressure and pulse rate measurements. The assessment will be performed after ECG, with the allowed time window of within 3 hr before dose administration for predose time point, ±20 minutes for the 4 hr post-dose, and ±30 minutes for 24 hr, 48 hr and 72 hr post-dose.

e. Electrocardiograms are to be performed as close to PK sampling time as possible and followed by vital assessment. The allowed time window will be within 3 hr before dose administration for Predose, and ±20 minutes for the 4 hr postdose, and ±30 minutes for the 72 hr postdose. Assessments will include an evaluation of heart rate, QT, and QTc intervals. RR interval should be recorded during each ECG assessment in order to calculate QTcF. ECGs are to be

Statistical Analysis Plan**Sponsor:** BeiGene, Ltd.**Protocol Number:** BGB-Sitravatin b-101

performed prior to collection of vital signs and PK sample collection blood draws. Single 12-lead ECGs will be repeated twice, and an average taken of the 3 readings, if either of the following criteria apply: QTcF >500 msec OR QTcF change from the baseline (predose) is >60 msec.

f. Full physical examination at Check-in for Period 1; symptom-directed physical examination at Check-in for Period 2.

g. Symptom-directed physical examination.

3. Analysis Sets

The analysis sets of interest are:

- Safety Analysis Set
- PK Concentrations Analysis Set
- PK Parameters Analysis Set
- Relative Bioavailability Analysis Set.

Each of the analysis sets, as well as the criteria for exclusion from each set will be described in the following sections.

Screen failure data will not be included in any output.

3.1 Safety Analysis Set

The Safety Analysis Set is defined as the set of subjects who received at least one dose of sitravatinib.

The following are reasons for exclusion from the Safety Analysis Set:

- Subject did not provide informed consent.
- Subject did not receive at least one dose of sitravatinib.

The Safety Analysis Set will be used as the analysis set for all baseline characteristics, disposition, and safety outputs.

3.2 Pharmacokinetic (PK) Concentrations Analysis Set

The PK Concentrations Analysis Set is defined as all subjects who received at least one dose of sitravatinib and have at least one quantifiable concentration of sitravatinib.

The following are reasons for exclusion from the PK Concentrations Analysis Set:

- Subject did not receive at least one dose of sitravatinib.
- Subject does not have at least one quantifiable concentration of sitravatinib.

At the discretion of the pharmacokineticist, a concentration value may also be excluded if the deviation in sampling time is of sufficient concern or if the concentration is anomalous for any other reason.

The PK Concentrations Analysis Set will be used as the analysis set for the PK concentration outputs.

3.3 Pharmacokinetic (PK) Parameters Analysis Set

The PK Parameters Analysis Set is defined as all subjects who received at least one dose of sitravatinib and have at least one PK parameter of sitravatinib.

The following are reasons for exclusion from the PK Parameters Analysis Set:

- Subject did not receive at least one dose of sitravatinib.
- Subject does not have at least one sitravatinib PK parameter.
- Subject experienced an event that may affect their PK profile (e.g., has an AE of vomiting that occurs at or before 2 times median T_{max}).

At the discretion of the pharmacokineticist, PK parameter results may also be excluded from the analysis if it is not sufficient to characterize the PK profile (e.g. percentage of AUC extrapolation >20%).

The PK Parameters Analysis Set will be used as the analysis set for the PK parameter outputs.

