8.2. Analysis Set

PK Concentration Analysis Set: all subjects who received at least 1 dose of sitratavinib and have at least 1 quantifiable concentration of sitratavinib.

PK Parameter Analysis Set: all subjects who received at least 1 dose of sitratavinib and have at least 1 PK parameter of sitratavinib. Subjects who experience events that may affect their PK profile (eg, has an AE of vomiting that occurs at or before 2 times median T_{\max}) may be excluded from the PK analysis. At the discretion of the pharmacokineticist, a concentration value may also be excluded if the deviation in sampling time is of sufficient concern or if the concentration is anomalous for any other reason.

Relative bioavailability Analysis Set: the subset of the PK Parameter analysis set and is defined as all subjects in PK Parameter analysis set who have at least one primary PK parameter (AUC_{0-t} , $AUC_{0-\infty}$ and C_{\max} of sitratavinib) in both periods.

Safety analysis set: the safety analysis population is defined as all subjects who received at least 1 dose of sitratavinib.

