4.3 Pharmacokinetic Parameters

The PK parameters described in this section will be derived based on the plasma sitravatinib concentration-time profiles as observed after the study drug administrations on Day 1 of each treatment period. The parameters will be calculated separately for each treatment period based on concentrations collected during the specific period.

BLQ concentrations observed prior to the maximum observed concentration (C_{max}) for the specific period will be set to zero and BLQ concentrations observed after C_{max} will be treated as missing in all

Sponsor: BeiGene, Ltd.
Protocol Number: BGB-Sitravatinib-101

parameter calculations. Derivations will be based on the actual elapsed time (hours) since the study drug administration in the specific period.

The pharmacokinetic concentrations will be processed using standard noncompartmental analytical procedures to derive the required parameters. The software used for the analysis will be Phoenix™ WinNonlin® v8.2 (Pharsight Corporation, USA).

The PK parameters described in Table 4 will be derived for each period provided that the required concentrations data are available. Supporting PK parameters (used to derive or assess the validity of $t_{1/2}$ and associated parameters) which include R^2 , number of points for estimation of k_{el} and $\%AUC_{ext}$ will only be listed and not included in the summary tables.

Table 4 Plasma PK Parameters

PK Parameter (Unit)	Method
C_{max} (ng/mL)	Maximum observed plasma concentration.
t_{max} (h)	Time to reach maximum plasma concentration.
AUC_{0-t} (h*ng/mL)	Area under the plasma concentration-time curve from the time of the dose administration to the time of the last measurable concentration calculated by the linear up log down trapezoidal method.
$t_{1/2}$ (h)	Elimination half-life associated with the terminal slope (k_{el}) of the semilogarithmic drug concentration-time curve, calculated as $0.693/k_{el}$.
AUC_{0-inf} (h*ng/mL)	Area under the plasma concentration-time curve from the time of the dose administration to time infinity calculated by the linear up log down trapezoidal method.
CL/F (L/h)	The apparent total clearance.
V_z/F (L)	The apparent total volume of distribution.
R^2 (%)	R-squared.
No. of Points (%)	No. points for determination of k_{el} .
k_{el} (1/h) (%)	Apparent terminal elimination rate constant.

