6.9 Pharmacokinetic Analyses

6.9.1 Plasma Concentrations

The analysis of the PK concentration data will be based on the PK Concentrations Analysis Set.

The plasma sitravatinib concentrations data will be summarised by treatment group and nominal collection time points using the statistics described in Section 5.1.3. BLQ concentrations that occurred prior to C_{max} will be set to 0, and treated as missing otherwise, for the calculation of summary statistics. Zero values will be treated as missing for the calculation of the geometric statistics. Missing values will be omitted from the calculation of descriptive statistics.

Figures of the individual plasma concentrations vs. actual time profiles (both treatment groups for each subject on the same plot) will be presented on a linear and a log-linear scale. All concentration for both treatment groups will also be presented in the same spaghetti plot presented on a linear and a log-linear scale. BLQ concentrations that occurred prior to C_{max} will be set to 0 and treated as missing otherwise in the linear plots. BLQ concentrations will be set to missing in the log-linear plots.

Mean concentration profiles vs. nominal time curves will be presented on a linear and log-linear scale. Both treatment groups will be presented on the same plot. Standard deviation bars will also be presented.

All plasma concentration data will be listed, and the listing will include the calculated elapsed time since the study drug administration in the specific period and the time deviations between the actual and planned sample collection times.

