6.9.2 Pharmacokinetic Parameters

The calculated plasma PK parameters described in Section 4.3 will be summarised by treatment group using the statistics described in Section 5.1.3. The summary tables will be based on the PK Parameters Analysis Set.

Relative bioavailability will be summarised separately based on the Relative Bioavailability Analysis Set.

The analysis of the relative bioavailability between the two different formulations of sitravatinib (sitravatinib MSC as test and sitravatinib FBC as reference) will be based on the dose-dependent parameters AUC_{0-inf} , AUC_{0-t} and C_{max} . The \log_e -transformed parameters will be analyzed separately using a mixed effect model (data permitting) with the treatment group (formulation), sequence and period as fixed effects and subject nested within sequence as a random effect. The geometric means (exponentiated least squares means) and the associated 90% confidence intervals for each treatment group and the geometric mean ratio (exponentiated difference between sitravatinib MSC least-squares mean as test and sitravatinib FBC least-squares mean as reference) and the associated 90% confidence interval will be presented. The geometric mean ratios and the associated confidence

Sponsor: BeiGene, Ltd.

Protocol Number: BGB-Sitravatinib-101

intervals will be expressed as percentages. Bioequivalence will be concluded if the 90% confidence intervals of the geometric mean ratios of all three parameters lies entirely within the bioequivalence interval of 80% to 125%. Refer to Appendix 3 for the SAS® code that will be used for the analysis. The analysis will be based on the Relative Bioavailability Analysis Set.

The analysis will also be repeated based on the dose-normalized AUC_{0-inf} , AUC_{0-t} and C_{max} results.

The parameters AUC_{0-inf} , AUC_{0-t} and C_{max} will also be presented graphically by means of box-and-whiskers plots. The results for the two treatment groups will be presented on the same plot. The dose-normalized AUC_{0-inf} , AUC_{0-t} and C_{max} results will also be plotted separately. The plots will be based on the Relative Bioavailability Analysis Set.

All parameter results will be listed based on the PK Parameters Analysis Set, and any results that may have been excluded from the summary tables will be flagged. The SAS® outputs generated by the respective models will be presented in listings.

7. Changes to the Planned Analyses

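### The PK-event exclusion in SAP 3.3 removes the whole subject instead of the affected period, so an unaffected parameter profile leaves the descriptive tables and neither period's parameters are listed

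*SAP*

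**What the plan says.** SAP 3.3 defines the PK Parameters Analysis Set as a set of subjects. One listed reason for exclusion is "Subject experienced an event that may affect their PK profile"; the example is vomiting no later than twice the median Tmax. No period is mentioned. The same section adds that "The PK Parameters Analysis Set will be used as the analysis set for the PK parameter outputs". SAP 6.9.2 applies the set to the summaries and also states that "All parameter results will be listed based on the PK Parameters Analysis Set", with a flag for results left out of the summary tables.

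SAP 4.3 shows that the natural unit is smaller: "The parameters will be calculated separately for each treatment period".

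The concentration side has no matching rule. Under SAP 3.2 the reasons for exclusion are no dose, or "Subject does not have at least one quantifiable concentration of sitravatinib". Single values may also be removed at the pharmacokineticist's discretion, including "if the concentration is anomalous for any other reason". SAP 6.9.1 says: "The analysis of the PK concentration data will be based on the PK Concentrations Analysis Set".

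The subject-level wording comes from Protocol 8.2, which says that subjects with such events "may be excluded from the PK analysis". The SAP turns this into a listed reason for exclusion, and SAP 7.1 reports no changes from the protocol.

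**The concern.** In a two-period crossover, vomiting after one dose compromises one profile. It says nothing about the same subject's profile in the other period, on the other formulation. A rule written by subject discards that second profile from the parameter tables for no pharmacokinetic reason.

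Two further effects follow. First, the flag promised in SAP 6.9.2 can mark a result that was left out of a summary, but it cannot mark a subject who is outside the listing's own population. His parameters from both periods therefore appear in no planned parameter output. Second, the compromised profile remains by default in the concentration table and mean curves, so the parameter and concentration summaries for one formulation rest on different profiles.

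At stake are the descriptive summaries of the primary PK parameters, their consistency with the concentration summaries, and the completeness of the parameter listing.

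**Working it through.** **Inputs.** At most 26 subjects enrolled and 24 completers (Protocol 8.1, SAP 2.4); two profiles per completer; both periods required for the Relative Bioavailability Analysis Set (SAP 3.4); within-subject CV 40%, true ratio 95-105%, limits 80-125%, stated probability 92% (SAP 2.4). The documents give neither the number of subjects with an event, *k*, nor the fraction of exposure lost, *f*. Both are assumptions below.

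**1. The plan's own figure.** For a point estimate in a 2x2 crossover, SE = s x sqrt(2/N). With s = 0.40 and N = 24, SE = 0.1155. At a true ratio of 0.95:

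P = Phi[(ln 1.25 - ln 0.95)/0.1155] - Phi[(ln 0.80 - ln 0.95)/0.1155] = 92.3%.

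At 1.05 the result is 92.5%. With s = sqrt(ln(1 + 0.40^2)) = 0.385 the results are 93.2% and 93.4%. The stated 92% is reproduced.

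**2. Profiles kept.** Suppose *k* of 24 completers have an event in one period only. Parameter profiles kept are 2 x (24 - k) under the subject rule and 48 - k under a period rule. Paired subjects are 24 - k under either.

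| k | Subject rule | Period rule | Paired subjects, either rule | P at ratio 0.95, s = 0.40 |
|---|---|---|---|---|
| 1 | 46 | 47 | 23 | 91.7% |
| 2 | 44 | 46 | 22 | 91.1% |
| 3 | 42 | 45 | 21 | 90.5% |

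The period rule recovers one profile per affected subject and leaves the ratio analysis as it was. With all 26 subjects contributing, one profile is 1/26 = 3.8% of those on the unaffected formulation.

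**3. Effect on the mean concentration curve.** SAP 6.9.1 plots mean profiles with standard deviation bars, most naturally arithmetic means. If *k* of 26 otherwise average subjects each lose a fraction *f* on the same formulation, the mean falls by f x k/26:

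| f | k = 1 | k = 2 |
|---|---|---|
| 25% | 1.0% | 1.9% |
| 50% | 1.9% | 3.8% |
| 75% | 2.9% | 5.8% |

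The geometric mean in the concentration table falls by 1 - (1 - f)^(k/26), which runs from 1.1% (f = 25%, k = 1) to 10.1% (f = 75%, k = 2). All these figures assume the same proportional loss at every time point. Median Tmax was about 3 to 8 hours in patients (Protocol 1.3.2), so the vomiting window would be roughly 6 to 16 hours, and late vomiting would leave earlier samples untouched.

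**The case against.** The strongest reply is that nothing in the study's conclusion turns on this. SAP 3.4 requires a primary parameter in both periods, so the subject leaves the ratio analysis under either rule. That stands in full. A reader might infer that the subject-level rule biases or weakens the primary comparison; the documents do not support that.

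A reader might also infer that the data are lost, or that the exclusion is hidden. Neither is so. SAP 6.1 lists each subject's inclusion in or exclusion from every set, with reasons. SAP 6.9.1 lists all concentrations with elapsed times and plots each subject's two profiles together. The excluded subject stays in the concentration set, so his Cmax can be read off and his AUC recomputed. What remains is narrower: the parameters themselves are neither listed nor flagged.

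On the concentration side, the discretionary clause in SAP 3.2 could remove samples taken after vomiting, and keeping the profile has some merit because it makes the exclusion checkable. That is fair. But the clause is optional, works value by value and does not name vomiting, so the reader of a mean curve cannot know which course was taken.

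The event may never happen. In the earlier healthy-subject study, safety data on 16 subjects showed three Grade 1 AEs, none of them vomiting (Protocol 1.3.1). The sample is small, but it is the only healthy-subject evidence in the documents.

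Finally, the subject-level wording is the protocol's, and the contrast between its permissive phrasing and the SAP's list of reasons is thin, since both still need a judgement that an event may have affected the profile.

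**Conclusion.** The concern holds in a limited form. As written, each subject with a PK-affecting event in one period loses two parameter profiles from the descriptive tables instead of one, and his parameters from both periods drop out of the parameter listings. His affected concentrations stay in the concentration summaries unless someone chooses to remove them.

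The benefit of correcting this is confined to the descriptive parameter summaries, the completeness of the parameter listing and clarity about the mean curves. It does not extend to the geometric mean ratio or its confidence interval. The size is one of up to 26 profiles per event, which follows from the enrolment ceiling. The 1.0% to 5.8% shift in the mean curve is illustrative only, because it rests on an assumed 25-75% uniform loss in one or two subjects on the same formulation. The 10.1% figure should not be read as a shift in the plotted curve: it belongs to the geometric mean at the extreme of those assumptions.

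**What to change.** - **SAP 3.3:** apply the exclusion per subject-period. Keep the subject in the PK Parameters Analysis Set and leave only the affected period's parameters out of the summaries.
- **SAP 3.4:** state that parameters from an excluded period do not count as available, so that the subject still leaves the Relative Bioavailability Analysis Set.
- **SAP 6.9.2:** list every computed parameter, with excluded values flagged and the reason given.
- **SAP 3.2 and 6.9.1:** state whether the affected profile enters the concentration summaries and mean figures, and footnote it if it is kept.
- **SAP 7.1:** record the period-level rule as a departure from Protocol 8.2.

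A run of the mixed model with these subjects included is a separate, optional sensitivity analysis; this point does not depend on it.

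The cost is a few sentences in the SAP and one flag at subject-period level. SAP 3.3 already allows individual parameter results to be excluded, for example for a large extrapolated AUC, so the mechanism exists. Trial conduct does not change.
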